The primary purpose of this amendment is to update the patient randomization and clarify enrollment of treatment dose groups. Because some participating countries did not have regulatory approval for all dose levels, the Sponsor has decided to provide all sites the opportunity to enroll patients in their region at an approved dose level. To facilitate this, patients will continue to be randomized through the IVR system; however, it may not necessarily be equally in a 1:1:1 manner. Additionally, the Sponsor decided to assess the safety and efficacy of the higher dose levels prior to deciding to conduct the 80-mg treatment group.

Additionally, Protocol Section 8.5.3 was updated to provide clarification to contact the Sponsor Medical Monitor prior to any modifications in safety monitoring.

These updates do not change the safety and efficacy objectives of the trial.

Also, administrative clarifications and corrections for typographical errors have been made throughout the protocol to improve the overall clarity of the original protocol; however, these changes do not impact subject safety, exposure, or the overall study design.

[figure not shown]
The following modifications to Protocol ISIS 766720-CS5 have been made. Changes to the protocol language are **bolded** and underlined. The table below provides a list of changes to the protocol:

Protocol Section	Description of Change
Protocol Synopsis: Number of Patients	Approximately 40 patients are planned to be randomized in the study. Thirty-six (36) patients (12 in each treatment group) in the per protocol set (PPS) are needed to complete the Treatment Period and the primary efficacy endpoint. Patients will be randomized equally (1:1:1) to 1 of the 3 treatment groups (80 mg, 120 mg, 160 mg). Patients will be enrolled to either the 120 mg or the 160 mg groups initially. After review of the safety and efficacy data in approximately 50% of the patients, the 80 mg group may be enrolled. If the 80 mg treatment group is not conducted, approximately 30 patients will be randomized.

Protocol Section	Description of Change
Protocol Synopsis: Statistical Considerations	Eligible patients will be stratified based on screening serum IGF-1 level ($> 2.5 \times \text{ULN}$ vs. $\leq 2.5 \times \text{ULN}$ age and sex adjusted by the central lab) and then patients will be randomized to 1-of-3 one of the treatment groups (ISIS 766720 80 mg, 120 mg or 160 mg). in a 1:1:1 ratio.

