3.3. Number of Patients

Approximately 40 patients are planned to be randomized in the study. Thirty-six (36) patients (12 in each treatment group) in the per protocol set (PPS) are needed to complete the Treatment Period and the primary efficacy endpoint. [REDACTED]

[REDACTED]

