10.6.3. Efficacy Analysis

The primary analysis will be the comparison of percent change from Baseline to Week 27 in serum IGF-1. The null hypothesis of no percentage change in serum IGF-I levels from Baseline to Week 27 will be tested for each treatment group in the PPS. The data will be analyzed using a one-sample t-test with an alpha level of 5%. Ninety-five percent (95%) confidence interval of estimated percent reduction within treatment group will also be provided. In the case data departs substantially from normality, the nonparametric test will be employed instead. The primary analysis will take place after all patients complete Treatment Period and the database has been locked.

The primary efficacy endpoint will also be assessed, as a secondary analysis, in the FAS.

Additional secondary efficacy analyses are:

- change and percent change from Baseline to each schedule post-baseline visit in serum IGF-1 by the ISIS 766720 treatment groups in the PPS and FAS. The data will be analyzed in a similar way to the primary analysis
- proportion of patients achieve normalized IGF-1 levels to within 1.2 times of gender and aged limits within each ISIS766720 treatment groups will be assessed by an exact binomial test in the PPS and FAS.
- proportion of patients achieve normalized IGF-1 levels to within 1.0 times of gender and aged limits within each ISIS 766720 treatment groups will be assessed by an exact binomial test in the PPS and FAS

Further details will be described in the Statistical Analysis Plan (SAP).

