3.2. General Overview of Analyses

3.2.1. Statistical Methods

Descriptive summary statistics including number of patients, mean, median, standard deviation, standard error of mean, 25th percentile, 75th percentile, minimum, and maximum for continuous variables, and counts and percentages for categorical variables will be provided to summarize most data. The study outcomes will be summarized by treatment groups. The efficacy endpoints

will be assessed on the FAS and PPS with the latter being the basis for the primary efficacy analysis. The safety analyses will be performed on the Safety Set. Pharmacokinetic analysis will be conducted in the PK Set.

For the continuous outcomes, the data will be analyzed using one-sample t-test to evaluate the estimate percent changes are different than zero. For the categorical outcomes, the data will be analyzed by using one-sample binomial Exact test ([Clopper and Pearson 1934](#)) to evaluate whether the estimate proportions are deviated from zero. The normality assumption for one-sample t-test model will be assessed by the Shapiro-Wilk test. In the case of data departs substantially from normality, the nonparametric Wilcoxon signed rank test will be applied instead. All statistical tests will be conducted using 2-sided tests with 5% Type I error rate unless otherwise stated. Where appropriate, P-values will also be provided as an indicator to summarize how much deviation from zero within each treatment group based on the statistical tests.

Additional summary of between treatment group comparison may be provided. Treatment group and the stratification factor are included as the independent variables in the statistical model while comparing among treatment groups. For the continuous endpoints, the ANCOVA or ANOVA model will be applied depending on the independent variables or van Elteren test if the data departs substantially from normality. For the dichotomous endpoints, logistic regression will be used instead.

Additional subject listings included case report form (CRF) data and derived outcomes from the data may be presented.

Baseline definition:

Due to the variance of IGF-1 between Screening and Day 1, baseline of IGF-1 is defined as the average value of Screening and Day 1 prior to the first administration of ISIS 766720. Multiple results with the same visit label will be averaged first, and baseline IGF-1 will be calculated as IGF-1 at Screening plus IGF-1 at Day 1 divide by 2.

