3.4. Secondary Analyses

3.4.1. Secondary Endpoint Definitions

Normalized IGF-1 level is defined as the ratio of the serum IGF-1 level and patient's upper limit of normal (ULN). The ULN will be varied among patients due to gender and age. Patients whose calculated ratios at scheduled visits are less than or equal to 1.2 or 1.0 will be deemed as achieving normalized IGF-1 at that scheduled visit.

For change from Baseline, non-missing IGF-1 measures over time will be compared to their baseline.

Patients without IGF-1 measure at a scheduled visit will not be imputed for that scheduled visit.

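### If the optional between-dose comparison of IGF-1 normalisation is run, the SAP's logistic regression makes no provision for separation, a material risk at 12 to 15 patients per group

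*Combined protocol and SAP*

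**What the plan says.** SAP 3.2.1 introduces the comparison as optional: "Additional summary of between treatment group comparison may be provided". If it is done, "Treatment group and the stratification factor are included as the independent variables in the statistical model while comparing among treatment groups". Continuous endpoints get ANCOVA or ANOVA, with the van Elteren test as a fallback for non-normal data. For responder endpoints the SAP says only: "For the dichotomous endpoints, logistic regression will be used instead". It names no exact or penalised version and no rule for empty cells or non-convergence.

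The responder endpoints are defined in SAP 3.4.1: patients whose ratio of IGF-1 to their own ULN is "less than or equal to 1.2 or 1.0 will be deemed as achieving normalized IGF-1".

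The planned analysis of these endpoints is a different one. Protocol 10.6.3 says the proportions "within each ISIS766720 treatment groups will be assessed by an exact binomial test in the PPS and FAS". SAP 3.2.1 names the same one-sample exact test for categorical outcomes, and SAP 3.4.2 adds a proportion with a 95% confidence interval. SAP 3.4.2 does not mention logistic regression.

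On size, protocol 3.3 states: "Thirty-six (36) patients (12 in each treatment group) in the per protocol set (PPS) are needed". The list of changes for Amendment 3 adds: "If the 80 mg treatment group is not conducted, approximately 30 patients will be randomized". On allocation it says that "it may not necessarily be equally in a 1:1:1 manner".

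**The concern.** The stratum boundary is 2.5 x ULN, and patients may enter with up to 5 x ULN. A patient above the boundary must lose more than 60% of IGF-1 to reach 1.0 x ULN, or more than 52% to reach 1.2 x ULN, while the SAP plans on a mean fall of 27.5%. Few high-stratum patients would respond on those figures. With about 12 patients per group, a stratum or a whole dose group may have no responders.

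Maximum likelihood then pushes a coefficient to infinity. Software reports a very large estimate with an unusable standard error, or a convergence warning. Someone must then choose another method after seeing the data, in an open-label trial. At stake are the odds ratios between doses for normalisation, should the sponsor decide to report them.

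**Working it through.** **1. The plan's own sample size.** Inputs from SAP 3.3.3: reduction 27.5%, SD 30%, two-sided 5%, one-sample t-test, 10% drop-out. Noncentrality for n = 12 is (27.5/30) x √12 = 3.18. Noncentral-t power is 78.2% at n = 11 and 82.4% at n = 12, so 12 is the smallest n that reaches 80%. For the total, 36/0.9 = 40. Both figures reproduce.

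**2. Chance that one patient normalises.** The fall needed is 1 - threshold/baseline. The chance is Φ((27.5 - fall needed)/30), with the fall in per cent.

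| Baseline | Fall to 1.0 x ULN | Chance | Fall to 1.2 x ULN | Chance |
|---|---|---|---|---|
| 2.5 x ULN | 60% | 14% | 52% | 21% |
| 5 x ULN | 80% | 4% | 76% | 5% |

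Averaged over the assumed baselines in step 4, response is about 7-10% (1.0 x ULN) and 10-14% (1.2 x ULN) in the high stratum, against 26-31% and 39-44% in the low stratum.

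**3. Rough check by hand for 1.0 x ULN.** Suppose 12 of 36 patients are in the high stratum, four per group (an assumption), with response 9% high and 28% low.
- No responder in the whole high stratum: 0.91^12 = 32%. The stratum coefficient is then infinite, but the dose contrasts are still estimated from the low stratum.
- No responder in one given dose group: 0.72^8 x 0.91^4 = 5.0%. In at least one of three groups: 1 - 0.950^3 = 14%. A dose contrast is then infinite.

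**4. Simulation.** Each case uses 4,000 trials. Percent change is Normal(-27.5, 30), truncated at -95%, equal in all groups. Groups are of equal size. The documents give no baseline distribution, so five were assumed: uniform 1.3-5, uniform 1.3-3.5, and lognormal (log-SD 0.4, truncated to 1.3-5 x ULN) with median 1.8, 2.0 or 2.5. Separation in the model with group and stratum was detected by linear programming. Any = some coefficient non-finite; dose = a dose contrast non-finite.

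| Design | Baseline | 1.0: any | 1.0: dose | 1.2: any | 1.2: dose |
|---|---|---|---|---|---|
| 3 x 12 | uniform 1.3-5 | 50% | 44% | 26% | 22% |
| 3 x 12 | uniform 1.3-3.5 | 32% | 19% | 13% | 5% |
| 3 x 12 | median 1.8 | 45% | 9% | 27% | 2% |
| 3 x 12 | median 2.0 | 39% | 12% | 21% | 3% |
| 3 x 12 | median 2.5 | 39% | 28% | 18% | 10% |
| 2 x 15 | uniform 1.3-5 | 37% | 22% | 20% | 10% |
| 2 x 15 | uniform 1.3-3.5 | 29% | 7% | 14% | 1% |
| 2 x 15 | median 1.8 | 49% | 3% | 34% | 0% |
| 2 x 15 | median 2.0 | 42% | 4% | 28% | 1% |
| 2 x 15 | median 2.5 | 32% | 11% | 16% | 3% |

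The Monte Carlo standard error is below 1 point, and runs of the lowest 1.0 x ULN case gave 28% or 29%. If 30 patients are randomised to two groups and 10% drop out, about 13 per group remain (30 x 0.9/2 = 13.5). With 13 per group and median 1.8, some coefficient is non-finite in 54% (1.0 x ULN) and 39% (1.2 x ULN), the top of the ranges.

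**5. Sensitivity, 3 x 12 unless stated.**
- Assumed mean falls of 15, 27.5 and 40% by dose: any about 38-57% (1.0) and 17-35% (1.2); dose contrast 19-53% and 5-32%.
- SD 20% instead of 30%: any 44-88% over both thresholds.
- Mean fall of 50%, in 3 x 12 or 2 x 15: any about 1-10%.

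**The case against.** The strongest objection is that the model is optional and that nothing planned depends on it. This stands. A reader might infer that the trial could fail to answer its secondary objective. The documents do not support that: the objective is to evaluate the drug's effect on normalisation, not to compare doses. The specified analysis is an exact test and interval within each group, which can be computed with zero responders.

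A reader might also take the risk of any non-finite coefficient as the chance of losing the dose odds ratio. That too is unsupported. When only the high stratum has no responders, the infinite term is a nuisance coefficient and the dose contrasts stay finite. With two groups of 15 and equal effects, a dose contrast is lost in 3-22% (1.0 x ULN) or 0-10% (1.2 x ULN).

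Third, the SAP does not commit to unpenalised fitting or Wald tests; Firth and exact fits are also logistic regression, and the likelihood-ratio statistic stays finite under separation. This is correct, but unqualified logistic regression normally means maximum likelihood, and the SAP leaves the choice open until the data are seen.

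Finally, the simulation uses one baseline value both to assign the stratum and to start the percent change. In the SAP the stratum comes from Screening, while baseline is the mean of Screening and Day 1. A patient stratified as high can therefore have a lower baseline and respond more easily, which would reduce separation somewhat. The assumed baseline distributions matter in the same way, so only the ranges should be relied on.

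**Conclusion.** The point holds for the optional between-group model only. If that model is run with 12 to 15 patients per group and the SAP's planning values are right, some coefficient is non-finite in roughly 28-54% of trials for 1.0 x ULN and 13-39% for 1.2 x ULN. With equal effects, a dose contrast is non-finite in about 3-44% and 0-22%. These figures rest on equal group sizes and on assumed baseline distributions, and they fall to about 1-10% if the mean reduction is near 50%. Uneven allocation, which Amendment 3 permits, was not simulated.

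This is a minor gap in specification. The continuous endpoints have a named fallback and the responder endpoints do not. It does not threaten the primary analysis or the planned analysis of normalisation.

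**What to change.** In SAP 3.2.1, replace logistic regression for between-group comparisons of dichotomous endpoints with Firth-penalised logistic regression, keeping treatment group and IGF-1 stratum as terms, and report profile penalised-likelihood confidence intervals. The estimates are then finite in the separated data sets described above, and no method has to be chosen after the responder counts are known.

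The cost is one change of SAP wording and an option in standard software. Sample size, data collection and the within-group exact analysis stay as they are. The downside is slight shrinkage of the odds ratios towards one.

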Study Visit Schedule and Procedures	
Detailed information regarding the study procedures is outlined in Section 6 of protocol.
 
The study for an individual patient will generally consist of the following periods:
 
• A ≤ 6-week Screening Assessment Period• A 73-week Treatment Period: ISIS 766720 will be administered as a once monthly SC injection (except during Month 1 where a booster dose is administered on Day 15). The primary endpoint will be evaluated at 6 months (Week 27)• A 14-week Post-Treatment Evaluation Period 
Laboratory and other study procedures will be performed to assess eligibility during the Screening Periods.
 
In the Treatment Period patients will be randomized to a treatment group.
 
Safety and tolerability will be assessed biweekly in the first 17 weeks and monthly after Week 17. A primary endpoint visit will occur at Week 27 (6 months). Efficacy, exploratory endpoints and plasma PK assessments will be conducted periodically during the Treatment Period. During the Post-Treatment Period, safety, exploratory and PK will be assessed for 14 weeks. The 2-hour OGTT and GH response assessments will be performed (3×) during the study (see Section 6.2.2 for details). An MRI (3×) and Echocardiogram (2×) will be done. See Appendix A.
 
Assessment of acromegaly clinical symptoms, patient reported outcome, and ring size measurement will be monitored during the Treatment Period and the Post-Treatment Period.
 
All safety data including adverse events (AEs) and concomitant medications will be reviewed by the Sponsor's Medical Monitor or Designee on an ongoing basis throughout the trial.
 
Dose adjustments may be allowed after 17 weeks of treatment and only after consultation with Sponsor Medical Monitor (or Designee). If initiation of other acromegaly medication(s) is clinically indicated, according to the Investigator judgement, the patient will discontinue ISIS 766720 and enter the Post-Treatment Period. In order to allow the drug to reach therapeutic steady-state concentrations, it is recommended to wait until after Week 17 before initiating other acromegaly medications.
 
All patients will complete the 14-week Post-Treatment Period after their last dose.

Primary Endpoint	The primary efficacy endpoint is the percent change in IGF-1 from Baseline to Week 27.

[figure not shown]
PROTOCOL SYNOPSIS CONTINUED

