8.8. Discontinuation of Study Drug/Treatment

A patient must permanently discontinue study treatment for any of the following:

- The patient becomes pregnant. Report the pregnancy according to instructions in Section [9.4](#)
- The patient withdraws consent
- The patient experiences an AE that necessitates permanent discontinuation of ISIS 766720
- The patient develops laboratory test abnormalities that meet any of the stopping rules listed in Sections [8.6.1](#) to [8.6.3](#)
- The patient meets any of the following Exclusion Criteria (see Section [5.2](#)) after discussion with the Sponsor Medical Monitor (or appropriately qualified Designee)
 - Patient needing pituitary surgery or radiation during Treatment Period
 - Patient with a pituitary tumor that is worsening (e.g., either growing, or at risk of compressing or abutting the optic chiasm or other vital structures) as assessed by pituitary/sellar MRI protocol
 - Treatment with any other acromegaly medications

The reason for discontinuation of ISIS 766720 must be recorded in the electronic Case Report Form (eCRF) and source documentation.

Patients who discontinue ISIS 766720 should complete early termination from treatment visit (ETTX) and then enter the Post-Treatment Period) unless consent is withdrawn. Minimally, every effort should be made to complete the ETTX (see [Appendix A](#), Section [6.1.2](#)).

If the patient declines or is unable to participate in the above, the Investigator should clarify what type of follow-up the patient is agreeable to: in person, by phone/mail, through family/friends, via correspondence/communication with other physicians, and/or from review of the medical records. Wherever possible, these patients should continue to be followed up via the agreed means to collect information on AEs, concomitant medications and survival status. At the very least, the patient's status at the end of the protocol defined study period should be ascertained and documented wherever possible. The agreed means of follow-up will be documented in the patient records and the Sponsor notified.

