8.10.1. Concomitant Therapy

A concomitant therapy is any non-protocol specified drug or substance (including over-the-counter medications, herbal medications and vitamin supplements) administered between signing of informed consent and last visit (PTWk15/ETPT).

Allowed Concomitant Therapy

Any other medications deemed necessary by the Investigator are allowed except those listed in the disallowed concomitant therapy.

In the Post-Treatment Period, approved acromegaly medication may be added for patients with elevated IGF-1 (≥ 1.3) levels in consultation with the Investigator and Sponsor Medical Monitor or Designee.

Disallowed Concomitant Therapy

The following medications or interventions cannot be started during the Treatment Period: other approved or investigational medications for acromegaly (e.g., bromocriptine, cabergoline, pasireotide, quinagolide, octreotide (all formulations), pegvisomant, pasireotide, lanreotide (all formulations), dopamine agonist). If modification of acromegaly medication is considered, the recommendation is to wait until after Week 17 to allow ISIS 766720 to reach steady-state therapeutic concentrations and to ensure patient is on a maximal dose of ISIS 766720 per Section 8.7 prior to initiation of other acromegaly medications.

Use of anti-obesity agents or weight loss programs are not allowed prior to Week 27. Initiation of anti-obesity agents or weight loss programs after Week 27 may be considered after consultation with the Sponsor Medical Monitor or Designee

It is preferred for patients to maintain stable regimens of estrogen containing medications, antidiabetic medications and glucocorticoids throughout the study, however, changes to a stable regimen allowed at Screening may only be considered after consultation with the Sponsor Medical Monitor or Designee.

Any investigational therapeutic drug or device including other marketed agents at experimental dosages/utilities that are being tested—patient will be withdrawn.

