8.10.2. Concomitant Procedures

A concomitant procedure is any therapeutic intervention (e.g., surgery/biopsy, physical therapy) or diagnostic assessment (e.g., blood gas measurement, bacterial cultures) performed between signing of informed consent and the last visit (PTWk15)

Surgery and radiotherapy for pituitary adenoma during the trial is not allowed (see Section 5.2) and patients who undergo these procedures during the study will be early terminated from the Treatment Period and enter the Post-Treatment Period.

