Appendix A. Schedule of Procedures – Post-Treatment Period

Study Period	Post-Treatment Period (14 Weeks)			ETTX ^{1, 2}	ETPT ^{1, 2}
Study Week (Wk) from Last Dose	PTWk5	PTWk9	PTWk15	ETTX ^{1, 2}	ETPT ^{1, 2}
Study Day from Last Dose	PTD29 ²	PTD57 ²	PTD99 ²	NA	NA
Study Day from Day 1	533	561	604	NA	NA
Visit Window ±	7	7	7	NA	NA
Home Health Care Visit Option ³	X	X			
MRI/CT of sellar				X ¹³	
Echocardiogram				X ¹⁴	
AcroQoL			X	X	X
ASTS-M			X	X	X
EQ-5D			X	X	X
SF-36			X	X	X
Ring Size Measurement			X	X	X
Body Weight			X	X	X
Vital Signs ⁴	X	X	X	X	X
Physical Exam ⁵			X	X	X
ECG (12-Lead)			X	X	X
Adverse Events	X	X	X	X	X
Concomitant Medications	X	X	X	X	X
Pregnancy Test ⁶	X	X	X	X	X
Chemistry Panel (Fasting) ^{7, 8}	X	X	X	X	X
Hematology ⁸	X	X	X	X	X
Partial PD Panel: GH, IGF-1, GHBP ⁷	X	X			
Full PD Panel ⁷			X	X	X

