For other endpoints, baseline is defined as the last non-missing value prior to the first administration of ISIS 766720.

Analytical visits:

In general, all post-baseline data will be summarized using the visit labels provided in the data. Multiple results with the same visit label will be averaged for the continuous variables, and the worst result will be used for the categorical variables. Results with visit labels as “Unscheduled” will not be included in the by-visit summary tables and figures except for determining baseline and the incidence of abnormality lab summary including AST, ALT, platelet and renal but will be presented in data listings.

For patients who had last dose prior to treatment termination, PD results greater than 3 weeks after the last dose (the date of last dose + 21 days) up to treatment termination will not be included in the by-visit summary tables and figures. Also, for patients who started other acromegaly medications in the post-treatment period, PD results after the start date of acromegaly medication will not be included in the by-visit summary tables and figures.

Other situations, such as required additional confirmation, will be described separately in the related endpoint analysis approach.

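### The SAP's rule for dropping IGF-1 after rescue covers only drugs started in the post-treatment period, so comparable values after earlier drug starts, pituitary surgery or radiotherapy stay in the by-visit tables

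*Combined protocol and SAP*

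**What the plan says.** In this note, rescue means another acromegaly drug, pituitary surgery or pituitary radiotherapy.

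SAP 3.2.1 (Analytical visits) assigns results by label: "all post-baseline data will be summarized using the visit labels provided in the data". It then leaves two groups of PD results out of the by-visit tables and figures:

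- **21-day cut.** For patients whose last dose came before treatment termination: "PD results greater than 3 weeks after the last dose (the date of last dose + 21 days) up to treatment termination". This applies whatever the reason dosing stopped.
- **Rescue rule.** "for patients who started other acromegaly medications in the post-treatment period, PD results after the start date of acromegaly medication will not be included".

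IGF-1 is a PD result. It is in the post-treatment schedule (Protocol Appendix A: "Partial PD Panel: GH, IGF-1, GHBP" at PTWk5 and PTWk9, and the full panel at PTWk15, ETTX and ETPT).

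The protocol expects rescue and says where the patient goes next:

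- Section 8.10.1, on other acromegaly drugs: "The following medications or interventions cannot be started during the Treatment Period".
- Synopsis, if such a drug is clinically indicated: "the patient will discontinue ISIS 766720 and enter the Post-Treatment Period".
- Section 8.8 lists "Treatment with any other acromegaly medications" among the reasons to stop study drug, with the ETTX visit done before entry to the Post-Treatment Period.
- Section 8.10.2, on pituitary surgery and radiotherapy: "patients who undergo these procedures during the study will be early terminated from the Treatment Period and enter the Post-Treatment Period".

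The primary analysis uses the PPS, which excludes significant deviations expected to affect efficacy (SAP 3.2.2, 3.3.2). Secondary endpoints are summarised at each scheduled visit in FAS and PPS (SAP 3.4.2). Missing IGF-1 is not imputed (SAP 3.3.5).

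**The concern.** By adopting the rescue rule, the sponsor accepts that IGF-1 measured after another acromegaly drug no longer describes study drug alone. The same reasoning applies whichever period the drug was started in, and to surgery or radiotherapy on the tumour. The rule covers none of these other cases.

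Two patients with equally contaminated samples are therefore handled differently, depending on which side of treatment termination the drug began or on whether rescue was a drug or a procedure. What is at stake is the meaning of the by-visit IGF-1 and normalisation tables. In the FAS, some values would reflect another therapy. In the post-treatment rows, IGF-1 presented as measured after the last dose of study drug could be measured on a replacement drug or after a procedure.

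**Working it through.** **1. The plan's own figure.** SAP 3.3.3 assumes a 27.5% reduction, SD 30%, and a two-sided 5% one-sample t-test. Power comes from the noncentral t with n − 1 degrees of freedom and noncentrality (27.5/30)·√n. This gives 78.2% at n = 11 and 82.4% at n = 12, so 12 is the smallest n reaching 80%. Total: 36/(1 − 0.10) = 40. The stated sizes reproduce, and 12 is used as the arm size below.

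**2. Reach of the 21-day cut at Week 27.** Week 27 is Day 183 ± 7. The eight doses in the PPS definition are taken to fall on Days 1, 15, 29, 57, 85, 113, 141 and 169.

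| Last dose | Gap to Day 183 | Gap across the window | Cut removes it? |
|---|---|---|---|
| Day 169 | 14 | 7 to 21 | No |
| Day 141 | 42 | 35 to 49 | Yes, if not yet terminated |
| Day 113 | 70 | 63 to 77 | Yes, if not yet terminated |

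A Week 27 sample escapes the cut only if the patient was dosed on or near Day 169.

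**3. Which rule reaches which value (literal reading).**

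| IGF-1 value | 21-day cut | Rescue rule | Outcome |
|---|---|---|---|
| (1) Within 21 days of last dose, drug started during treatment | Not reached | Not reached | Kept |
| More than 21 days after last dose, before termination | Removes it | Not needed | Dropped |
| (2) Post-treatment, drug started before termination | Cut has ended | Not reached | Kept |
| Post-treatment, drug started after termination | Cut has ended | Removes it | Dropped |
| (3) Post-treatment, after surgery or radiotherapy | Cut has ended | Not named | Kept |

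**4. Group (2) on an ordinary path.** Take two patients with last dose on Day 141 and ETTX at the preferred 4 weeks, Day 141 + 28 = 169, taken as treatment termination. PTWk9 falls on Day 141 + 56 = 197. Suppose patient A starts another drug on Day 155 and patient B on Day 170 (start days chosen for illustration). At PTWk9, A has had 197 − 155 = 42 days on the other drug and B 197 − 170 = 27. B's value is dropped. A's, with the longer exposure, is kept.

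**5. Size.** The shift in a group mean is m·x/n for m affected patients, each with an extra fall of x percentage points. The documents give no rescue, surgery or radiotherapy rates and no x, so x = 10 to 40 is an assumption. At n = 12:

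- m = 1: 10/12 = 0.8 to 40/12 = 3.3 points.
- m = 2: 20/12 = 1.7 to 80/12 = 6.7 points.
- One patient wrongly counted as normalised: 1/12 = 8.3 points on a responder rate.

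**6. Cost of a wider rule at Week 27.** Under the plan's assumptions, losing one value from a group of 12 leaves 78.2% power, and losing two leaves 73.3%.

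**The case against.** The best defence is that the SAP rule follows the protocol's own rescue path. Other acromegaly drugs are disallowed on treatment. If one is needed, study drug stops and the patient moves to the Post-Treatment Period, where the rule applies. A drug taken earlier is a deviation, and the PPS filter should remove an obvious one from the primary analysis. Needing surgery or radiation is itself a reason to discontinue, after which samples normally carry ETTX or post-treatment labels rather than Week 27. The 21-day cut removes many of the remaining values.

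Much of this stands. A reader might infer that all post-rescue values are credited to study drug and that the primary result is materially biased. The documents do not support that. For a Week 27 value to be affected, rescue must begin shortly before Week 27 in a patient dosed on or near Day 169, or in one kept on study drug, and must not be classed as a significant deviation. With a drug started on Day 176, for instance, only 183 − 176 = 7 days have passed by the Week 27 sample, so a large extra fall is unlikely. Nor do the documents define a persistence-of-effect endpoint or show that rescued patients are the poor responders. The direction of error is plausible but not established.

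It can also be argued that the post-treatment period starts at the last dose, because Protocol 3.4.3 and Appendix A count its visits from there. Patient A would then be covered. But Section 8.8 places ETTX before entry to that period, and the 21-day cut itself separates last dose from treatment termination. At best the wording is ambiguous, and no reading of it brings in surgery or radiotherapy.

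The defence does not protect the FAS. In the PPS it relies on judgement, because the significant deviations are not listed.

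**Conclusion.** The concern holds in limited form. The one rule keyed to rescue is tied to one period and one type of rescue, and the three kinds of value numbered in the working stay in if it is followed literally. The main effect is on the post-treatment and FAS by-visit tables of IGF-1 and normalisation. The Week 27 primary result in the PPS is exposed only in narrow cases. The SAP also does not say whether either exclusion governs the Week 27 t-test, since both are written for by-visit tables and figures.

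The size cannot be computed without event rates. The 0.8 to 3.3 points for one affected patient of 12 is an illustration resting on the assumed 10 to 40 point extra fall. The Week 27 day counts assume on-schedule dosing, and group (2) assumes that the post-treatment period begins at treatment termination.

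**What to change.** Replace the rescue sentence in SAP 3.2.1 with a rule to this effect: PD results obtained after the earliest of (i) the start of any other acromegaly drug, (ii) pituitary surgery or (iii) pituitary radiotherapy, in any study period, are left out of by-visit summaries and of the Week 27 analyses of study-drug effect, and are listed with a flag. Keep the 21-day cut and state whether it too governs the Week 27 test.

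Add three items:

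- For the two Week 27 normalisation endpoints, a sensitivity analysis counting a patient as not normalised if rescue began on or before that patient's Week 27 sample. Rescue after that sample leaves Week 27 status unchanged.
- The number of values excluded for rescue, by visit and group.
- A sensitivity summary using all observed values.

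The cost is a short SAP edit and one derived flag. Medications and procedures are already recorded on the eCRF (Protocol 8.10). A few values leave the tables, with the power loss shown in the working if they are Week 27 values. Because missing IGF-1 is not imputed, dropping rescued patients from the percent-change means may itself favour the drug slightly. The exclusion counts and the all-values summary let a reader judge this.
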